5.3 Method for Assigning Subjects to Treatment Groups

Subjects will first receive niacin and for the second study they will receive intravenous saline as the placebo.

Preparation and Administration of Study Drug

Nicotinic acid will be received in powder form and compounded at Research Pharmacy following Compounding Procedures and an approved compounding formula sheet, for intravenous administration which runs in a Baxter infusion pump model Sigma Spectrum. The drug will be aliquoted in single dose amber vials of 10 mL each and refrigerated at a temperature of 2-8°C.

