5.8.4 Return or Destruction of Study Drug

All medications would be given on site. Any patient specific unused medication will be destroyed on site.

6 Study Procedures

Table 1 below lists all of the assessments and indicates with an "x" the visits when they are performed. Subjects should be seen for all visits on the designated day and time.

Subjects who are discontinued before completing the study, and those who withdraw prematurely from the study for any reason, should be scheduled for a visit as soon as possible, at which all of the assessments listed for the "end of Study" visit will be performed. Study visits will occur at Screening, Visit 1 and Visit 2/End of Study.

The maximum duration of the clinical investigation is up to 8 weeks from enrollment (signing of consent, which allows for a 14 day screening period).

Schedule of Events			
	Screening	Inpatient Visit 1	Inpatient Visit 2
Study Day	-14	0	28-56
Written informed consent	X		
History and demographics	X		
Concurrent med reconciliation	X		
Height	X		
Weight	X	X	X
Vitals	X	X	X
Laboratory tests ^a	X*		
Single-slice abdominal CT	X		
DEXA scan	X*		
Adverse event evaluation	X	X	X
Pregnancy test	X ^b	X ^c	
Study Agent (niacin administration)		X	
Insulin and glucose administration		X	X
Isotope administration		X	X
Resting energy expenditure		X	X
Muscle Biopsies		X	X
Adipose biopsies		X	X

a: Complete metabolic panel, CBC w/differential, Lipid Panel, HbA1C, liver function tests if not part of complete metabolic panel

b: Serum pregnancy test (women of childbearing potential) at screening

c: Urine pregnancy test (women of childbearing potential) ≤ 48 hours prior to study drug administration.

*Research DEXA scan, labs, and CT scan completed in the previous 3 months may be used in place of repeating these.

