end of the study. Resting energy expenditure will be measured by indirect calorimetry to permit interpretation of FFA flux data. A series of blood samples will be collected between 0830 and 0900 h to measure steady state plasma palmitate and glucose enrichment and concentrations.

The volunteers will then undergo a vastus lateralis muscle biopsy for measurement fatty acid metabolites and to provide material for the “pre-clamp” measures of insulin signaling and the niacin infusion will be tapered to 25% of their overnight dose.

Insulin regulation of muscle glucose uptake and fatty acid metabolism will be assessed using a primed, constant infusion of insulin at a dose of 1.0 mU/kg/min. Arterialized venous blood samples will be collected from the same retrograde IV catheter using the hot box with a temperature of 131 degrees Fahrenheit, to allow measurement of hormone, tracers and substrate concentrations over the 30 min prior to the insulin clamp and the last 30 min of the insulin clamp. Blood glucose will be measured every 10 min throughout to allow the glucose infusion rate to be adjusted to maintain euglycemia. Resting energy expenditure will be measured by indirect calorimetry to permit interpretation of FFA flux data. (79).

Adipose tissue biopsies will be collected from the abdominal region under local anesthesia using sterile technique (82) at the same time as the first and last muscle biopsies. The adipose tissue samples (2-3 g from each site) will be immediately rinsed of blood and transported to our laboratory (~ 3 min walk from the CRTU).

There we will divide the specimen into smaller aliquots for collagenase digestion to be used for cell sizing (83), and immunohistochemistry.

The volunteers will be able to order a general meal after the biopsies. After this, the participants will be discharged from the CRTU.

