All adverse events that do not meet any of the criteria for serious, should be regarded as **non-serious adverse events**.

Adverse Event Reporting Period

For this study, the follow-up period is up to 6 weeks from the 1st biopsy visit. Any adverse event occurring during the course of the study period will be reported.

Preexisting Condition

A preexisting condition is one that is present at the start of the study. A preexisting condition should be recorded as an adverse event if the frequency, intensity, or the character of the condition worsens during the study period.

General Physical Examination Findings

At screening, any clinically significant abnormality should be recorded as a preexisting condition. At the end of the study, any new clinically significant findings/abnormalities that meet the definition of an adverse event must also be recorded and documented as an adverse event.

Post-study Adverse Event

All unresolved adverse events should be followed by the sponsor-investigator until the events are resolved, the subject is lost to follow-up, or the adverse event is otherwise explained. At the last scheduled visit, the sponsor-investigator should instruct each subject to report, to the sponsor-

investigator, any subsequent event(s) that the subject, or the subject's personal physician, believes might reasonably be related to participation in this study.

Abnormal Laboratory Values

Research lab results taken between study drug administration and study completion are expected to be abnormal as a result of adipose tissue and muscle biopsies (catecholamines) done during the study. Screening lab values are reviewed by the physician principal investigator in the EMR and documented as reviewed in the EMR. Clinical lab results obtained by a primary care provider or other physician that is not involved in the study in the time that a participant receives the study drug will not be assessed for abnormality.

Hospitalization, Prolonged Hospitalization or Surgery

Any adverse event that results in hospitalization or prolonged hospitalization should be documented and reported as a serious adverse event unless specifically instructed otherwise in this protocol. Any condition responsible for surgery should be documented as an adverse event if the condition meets the criteria for an adverse event.

Neither the condition, hospitalization, prolonged hospitalization, nor surgery are reported as an adverse event in the following circumstances:

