8.2 Recording of Adverse Events

At each contact with the subject, the study team will seek information on adverse events by specific questioning and, as appropriate, by examination. Information on all adverse events will be recorded immediately in the source document, and also in the appropriate adverse event section of the case report form (CRF) or in a separate adverse event worksheet. All clearly related signs, symptoms, and abnormal diagnostic, laboratory or procedure results will be recorded in the source document.

Adverse events are considered events that are not already described as routine research risks in the consent form. We will not report pain at time of the biopsy as an AE, nor will we report bruising from biopsy or line placement procedures as these are nearly guaranteed to occur with all participants. All adverse events occurring during the study period will be recorded. The clinical course of each event would be followed until resolution, stabilization, or until it has been ultimately determined that the study treatment or participation is not the probable cause. Serious adverse events that are still ongoing at the end of the study period must be followed up, to determine the final outcome. Any serious adverse event that occurs during the Adverse Event Reporting Period and is considered to be at least possibly related to the study treatment or study participation will be recorded and reported immediately.

We will use the following standardized system for classification and grading of Adverse Events
http://evs.nci.nih.gov/ftp1/CTCAE/CTCAE_4.03_2010-06-14_QuickReference_8.5x11.pdf

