8.5 Stopping Rules

This is unlikely as our study does not involve a treatment or interventional strategy and subjects are dismissed on the day of biopsies. However the entire study may be discontinued at the discretion of the PI based on the occurrence of the following:

- Adverse effects that seriously impact the risk-benefit ratio have been observed
- Medical or ethical reasons affecting the continued performance of the study
- Difficulties in recruitment of subjects
- Any new information becomes available during the trial that necessitates stopping the trial
- Other situations that may warrant stopping the trial

Subjects will be informed that they are free to withdraw from the study at any time for any reason. The Principal Investigator (PI) may remove a subject from the study if, in the PI's opinion, it is not in the best interest of the subject to continue the study. Subjects may be discontinued due to a change in compliance with an inclusion/exclusion criterion that is clinically relevant and affects subject safety, occurrence of AEs, occurrence of pregnancy, or administration of non-permitted concomitant medication that might affect subject safety or study assessments/objectives. Notification of discontinuation will be made immediately to the Sponsor's Medical Monitor. In case of premature discontinuation of study participation, efforts will be made to perform end of study/follow up assessments. The date the subject is withdrawn from the study and the reason for discontinuation will be recorded on the subject's Case Report Form (CRF). All withdrawn subjects will be followed until resolution of any AEs or until any unresolved AEs are judged by the PI to have stabilized.

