B. Classification of AE Severity – AE's will be labeled according to severity which is based on their impact on the volunteer. An AE will be termed 'mild' if it does not have a major impact on the participant, 'moderate' if it causes considerable inconvenience and 'severe' if it causes a substantial disruption to the volunteer's well-being.

C. AE Attribution Scale – AE's will be categorized according to the likelihood that they are related to the study intervention. Specifically, they will be labeled either definitely, probably, possibly or unrelated to the study intervention.

D. Expected Risks –

Vascular access. Catheter insertion, intravenous infusion, and blood withdrawal are associated with small risks of phlebitis. This will be minimized by careful attention to sterile technique. As superficial phlebitis occurs, it will be treated conservatively with heat and, when appropriate, antibiotics. Superficial burns to the hand when using the hot hand technique to obtain arterialized venous samples are possible. This has not been a problem with the brief use of the heated box.

Muscle biopsies. The risks of these procedures include pain, hematomas, bruising, infection, and scarring of the biopsy site. In <1% of biopsies, a small area of numbness can develop due to cutting of a superficial sensory nerve. We advise volunteers that this can occur and make them aware that if it does, the re-growth of the nerve will take 6-12 months.

Risk Monitoring/Risk Reduction:

The risk of pain from muscle biopsies is virtually 100%, and the volunteers are given this information. We reduce the risk of infection by performing all biopsies under sterile conditions. We have yet to have an infection related to a muscle biopsy in the last 20 years. Nonetheless, each volunteer is told of the signs symptoms of infection and is told to call the study coordinator immediately should any of they occur. A record is kept of all adverse reactions to biopsies. If an increase in the number of adverse reactions relative to historical controls is observed during the course of a particular study a careful assessment of technique and approaches is made. The protocol might then be modified or additional instruction or supervision of the individual performing the biopsies could be undertaken. The subsequent results are then audited to determine how effective the intervention has been.

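### No one asks about adverse events after the last biopsy visit, and the reporting period can end before that visit takes place

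*Combined protocol and SAP*

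**What the plan says.** Section 8.2 sets the method of collection: "At each contact with the subject, the study team will seek information on adverse events by specific questioning". Section 6 (Study Procedures) lists the contacts: "Study visits will occur at Screening, Visit 1 and Visit 2/End of Study". The Schedule of Events puts Visit 1 on day 0 and Visit 2 on day 28 to 56, and marks an adverse event evaluation at all three visits and nowhere later.

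Both inpatient stays end on the biopsy day. Section 6.2 says of Visit 1, after the meal that follows the biopsies, "After this, the participants will be discharged from the CRTU". Section 6.3 repeats the same procedure at Visit 2. Section 8.5 confirms that "subjects are dismissed on the day of biopsies".

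Section 8.1 defines the reporting period: "the follow-up period is up to 6 weeks from the 1st biopsy visit".

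After the last visit the plan relies on participants coming forward. In Section 8.1, "At the last scheduled visit, the sponsor-investigator should instruct each subject to report" later events that the participant or a personal physician thinks may be related. Section 10.1 has volunteers told the signs of infection and told to call the coordinator at once. It also keeps a record of all adverse reactions to biopsies.

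**The concern.** Infection, hematoma and numbness at a biopsy site can appear or be noticed after discharge. For the first stay, someone asks about them at Visit 2. For the second stay, no one is scheduled to ask. The reporting period does not close the gap, because it is counted from the first biopsy visit and can expire before the second.

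Two planned uses of the counts are exposed. The annual report (Sections 8 and 8.6) addresses whether adverse event rates agree with pre-study assumptions. Section 10.1 reviews biopsy technique "If an increase in the number of adverse reactions relative to historical controls is observed". If delayed reactions to half of the biopsies are collected only passively, both could look more reassuring than they should. In addition, Section 8.2 ties immediate reporting of possibly related serious events to the reporting period. A serious event after a late Visit 2 would fall outside that sentence, although Sections 8.3 and 10.1 carry reporting duties of their own.

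**Working it through.** The plan gives no figure for completeness of collection, so there is none to reproduce. The check uses counts and dates.

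**Inputs**
- 20 participants (Section 3.2).
- Two muscle biopsies per stay, before and at the end of the clamp (Section 3.1). Adipose biopsies are taken at the same times as the first and last muscle biopsies (Section 6.2). Visit 2 repeats Visit 1 (Section 6.3).
- Visit 1 on day 0, Visit 2 on day *d* = 28 to 56 (Schedule of Events).
- Reporting period of at most 6 × 7 = 42 days from Visit 1 (Section 8.1).
- Numbness in under 1% of muscle biopsies (Section 10.1).

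**Step 1: biopsies affected.** In total 20 × 2 visits × (2 muscle + 2 adipose) = 160. At Visit 2, 20 × (2 + 2) = 80, of which 40 are muscle and 40 adipose.

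**Step 2: solicited follow-up and reporting period.** Solicited follow-up after Visit 1 is *d* days. After Visit 2 it is 0. The period remaining after Visit 2 is 42 − *d*.

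| Visit 2 on day | Solicited follow-up after Visit 1 | Solicited follow-up after Visit 2 | Reporting period left after Visit 2 |
|---|---|---|---|
| 28 | 28 days | 0 days | 42 − 28 = 14 days |
| 42 | 42 days | 0 days | 42 − 42 = 0 days |
| 56 | 56 days | 0 days | 42 − 56 = −14 days (already closed) |

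Even in the best row, the 14 days contain no scheduled contact.

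**Step 3: scale for one named harm.** For a rate *p* per muscle biopsy, the expected number of cases from Visit 2 is 40*p*, and the chance of at least one is 1 − (1 − *p*)^40, treating biopsies as independent. The plan gives only the 1% upper bound; the lower rates are assumptions.

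| *p* | Expected cases | Chance of at least one |
|---|---|---|
| 1% (upper bound) | 0.40 | 0.33 |
| 0.5% | 0.20 | 0.18 |
| 0.1% | 0.04 | 0.04 |

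Few events are at stake, but one case is plausible, and Section 10.1 gives 6 to 12 months for nerve re-growth.

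**Step 4: room for a later contact.** A contact 14 days after Visit 2 falls on day 28 + 14 = 42 to 56 + 14 = 70. The present period ends by day 42, so nearly all of that range lies outside it. Section 6 also caps the investigation at 8 weeks (56 days) from consent. If consent is on day −14, the cap falls on day 56 − 14 = 42, already before a late Visit 2.

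**The case against.** The strongest reply is that the harms are not lost. Volunteers are told to call about infection, are asked at the last visit to report later events, and known unresolved events are followed. Section 10.1 states that there has been no muscle-biopsy infection in 20 years. Section 6.3 aims at about 4 weeks between visits, which favors the day-28 row. This stands in part: the problem is under-ascertainment, not certain loss. But the call-in instruction names infection only, the last-visit instruction covers only events someone already suspects are related, and follow-up of unresolved events helps only when the event is known.

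It is also fair to say that an undercount against historical controls is not proven. The plan does not say how the historical reactions were collected; if by the same call-in route, like is compared with like. Nor is it clear which of these harms would count as adverse events, since Section 8.2 leaves out routine risks described in the consent form, which was not available for this review. The biopsy-reaction record in Section 10.1 has no such exclusion.

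A reader might infer more: that, because "Subjects will first receive niacin and for the second study they will receive intravenous saline as the placebo", the uneven follow-up makes niacin look worse than saline. The documents do not support that as a finding. They plan no niacin-versus-saline comparison of adverse events. The primary safety endpoint (Section 3.6) is symptoms during the niacin infusion, observed on site. Any ratio put on the imbalance would only restate an assumed self-report rate. The link to treatment also depends on the fixed order in Sections 3 and 5.3, whereas the Study Summary and Section 7.2 speak of randomization. Those passages need reconciling, but under either order it is the last visit that lacks follow-up.

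**Conclusion.** The gap is real and limited in size. Half of the trial's biopsies, 80 of 160, have no solicited follow-up after discharge, against 28 to 56 days for the other half. Depending on the date of Visit 2, the reporting period extends 14 days beyond it, ends on it, or has closed 14 days before it. The consequence is probable under-ascertainment of delayed biopsy harms in the adverse event review and the biopsy-reaction record. How large the undercount would be cannot be derived from the documents.

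The counts assume that all 20 participants complete both stays and that the Schedule of Events lists every planned contact. The dates take the full 6 weeks that Section 8.1 allows. The primary safety endpoint is unaffected, and no treatment comparison in the plan is biased by this. It is a cheap improvement to safety collection, not a threat to the trial's main result.

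**What to change.** - In Section 8.1, let the reporting period run to a fixed interval after the last biopsy visit instead of at most 6 weeks from the first.
- In Section 6, align the 8-week maximum with that period. With a 14-day interval the latest contact is day 70, or 70 + 14 = 84 days (12 weeks) after consent on day −14, which fits the upper limit of 3 months in Section 3.3.
- In the Schedule of Events and Section 8.2, add one scripted telephone contact at the same fixed interval (for example 14 days) after each inpatient visit. The script should name infection, hematoma and numbness, so that both stays are asked about alike.

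The cost is 20 × 2 = 40 short calls at most, apart from any for replaced participants, made by the existing coordinator, plus one schedule row and a slightly longer participation period. No dose, procedure or clinical rule changes.

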7.3 Subject Population(s) for Analysis

- All-treated population: Any subject entered into the study started the drug infusion and/or biopsy procedure.
- Protocol-compliant population: Any subject who was entered and received the protocol required study drug exposure and required protocol processing
- All-completed population: Only subjects who completed ALL study related procedures and follow-up will be included.

8 Safety and Adverse Events

Safety Review Plan –Study progress and safety will be reviewed quarterly with the research fellow and study coordinator and, because these are relatively small studies, the data summarized at 6 month intervals to allow for a large enough sample to assess outcomes. Progress reports, including patient recruitment and AE's will be provided to the Endocrine Research Committee following each of the 6 month reviews in the event that no participants are accrued in the study a report will not be provided. An annual report will be compiled and will include a list and summarization of adverse events at the time of the non-competing renewal. In addition, the annual report will address (1) whether adverse event rates are consistent with pre-study assumptions; (2) reason for dropouts from the study; (3) whether all participants met entry criteria; (4) whether continuation of the study is justified on the basis that additional data are needed to accomplish the stated aims of the study. The annual report will be reviewed by the Endocrine Research Committee and the results included in the minutes. These will be forwarded to the IRB and NIDDK and, if applicable, the Mayo CTSA CRU and FDA as indicated.

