8.1 Definitions

Unanticipated Problems Involving Risk to Subjects or Others (UPIRTSO)

Any unanticipated problem or adverse event that meets the following three criteria:

- Serious: Serious problems or events that results in significant harm, (which may be physical, psychological, financial, social, economic, or legal) or increased risk for the

subject or others (including individuals who are not research subjects). These include: (1) death; (2) life threatening adverse experience; (3) hospitalization - inpatient, new, or prolonged; (4) disability/incapacity - persistent or significant; (5) birth defect/anomaly; (6) breach of confidentiality and (7) other problems, events, or new information (i.e. publications, DSMB reports, interim findings, product labeling change) that in the opinion of the local investigator may adversely affect the rights, safety, or welfare of the subjects or others, or substantially compromise the research data, **AND**

- Unanticipated: (i.e. unexpected) problems or events are those that are not already described as potential risks in the protocol, consent document, not listed in the Investigator's Brochure, or not part of an underlying disease. A problem or event is "unanticipated" when it was unforeseeable at the time of its occurrence. A problem or event is "unanticipated" when it occurs at an increased frequency or at an increased severity than expected, **AND**
- Related: A problem or event is "related" if it is possibly related to the research procedures.

Adverse Event

An untoward or undesirable experience associated with the use of a medical product (i.e. drug, device, biologic) in a patient or research subject.

Serious Adverse Event

Adverse events are classified as serious or non-serious. Serious problems/events can be well defined and include;

- death
- life threatening adverse experience
- hospitalization
- inpatient, new, or prolonged; disability/incapacity
- persistent or significant disability or incapacity
- birth defect/anomaly

and/or per protocol may be problems/events that in the opinion of the sponsor-investigator may have adversely affected the rights, safety, or welfare of the subjects or others, or substantially compromised the research data.

Other important medical events are those that may not be immediately life threatening, but are clearly of major clinical significance. They may jeopardize the subject, and may require intervention to prevent one of the other serious outcomes noted above.

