8.3.1 Sponsor-Investigator reporting: notifying the Mayo IRB

The IRB requirements reflect the guidance documents released by the Office of Human Research Protections (OHRP), and the Food and Drug Administration (FDA) in early 2007 and are respectively entitled “Guidance on Reviewing and Reporting Unanticipated Problems Involving Risks to Subjects or Others and Adverse Events” and “Guidance for Clinical Investigators, Sponsors, and IRBs: Adverse Event Reporting – Improving Human Subject Protection.”

The sponsor-investigator will report to the Mayo IRB any UPIRTSOs and Non-UPIRTSOs according to the Mayo IRB Policy and Procedures.

According to Mayo IRB Policy any serious adverse event (SAE) which the Principal Investigator has determined to be a UPIRTSO would be reported to the Mayo IRB as soon as possible but no later than 5 working days after the investigator first learns of the problem/event:

The following information to collect when developing any forms for documentation of adverse events. Adverse events are considered events that are not already described as routine research risks in the consent form. We will not report pain at time of the biopsy as an AE, nor will we report bruising from biopsy or line placement procedures as these are nearly guaranteed to occur with all participants.

Information collected on the adverse event worksheet (*and entered in the research database*):

- Subject's name:
- Medical record number:
- Disease/histology (if applicable):
- The date the adverse event occurred:
- Description of the adverse event:
- Relationship of the adverse event to the research (drug, procedure, or intervention):
- If the adverse event was expected:
- The severity of the adverse event: (use a table to define severity scale 1-5**)
- If any intervention was necessary:
- Resolution: (was the incident resolved spontaneously, or after discontinuing treatment)

- Date of Resolution:

The sponsor-investigator will review all adverse event reports to determine if specific reports need to be made to the IRB and FDA. The sponsor-investigator will sign and date the adverse event report when it is reviewed. For this protocol, only directly related SAEs/UPIRTSOs will be reported to the IRB.

The use of a table of tables to define Relationship of an Event to the Research and to define the severity of each event.

Relationship Index

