- A. Protection of Subject Privacy – As part of the screening for these studies a medical history and physical examination will be performed, blood tests and body composition measurements will be made. None of the research data will be entered into the Mayo Electronic Medical Record. Any paper records that are generated are kept in [name] laboratory, which is locked at all times to prevent hallway entry. Because it often takes several months from the initial volunteer contact until the studies are complete, and because we need to communicate with multiple units (Radiology, Nuclear Medicine, Mayo CTSA CRTU, etc.) over the course scheduling, it is not possible to de-identify paperwork immediately. The paperwork with patient identifiers is kept in a locked room when not in use. Whenever possible the paper records generated will be such that once the study is complete the identifiers can be removed. A paper matching the subject name and other identifying information with the subject code should be kept in a separate place from the study information. No information will be given to anyone without permission from the subject. If samples are sent outside Mayo for analysis they are de-identified per Mayo Biospecimens Committee rules.
- B. Database Protection – Electronic research data will be kept on password protected computer servers that can be accessed only by those with human studies/privacy training and only with [name] direct approval. Electronic communication with outside collaborators involves only unidentifiable information.
- C. Confidentiality during AE Reporting –AE reports and annual summaries will not include participant-identifiable material. Each will include the identification code only.

IV. Adverse Event Information

- A. Definition - An adverse event (AE) is any untoward medical occurrence in a subject temporally associated with participation in the clinical study. An adverse finding can

include a sign, symptom, abnormal assessment (laboratory test value, vital signs, electrocardiogram finding, etc.) or any combination of these.

A Serious Adverse Event (SAE) is any adverse event that results in one or more of the following outcomes:

- Death
- A life-threatening event
- Inpatient hospitalization or prolongation of existing hospitalization
- A persistent or significant disability/incapacity
- A congenital anomaly or birth defect
- Important medical event based upon appropriate medical judgment

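### Sections 8.2 and 8.3.1 exclude consent-listed routine risks from the definition of an adverse event, contradicting sections 8.1 and 10.1 and leaving the reviewed AE rates open to undercounting

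*Combined protocol and SAP*

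**What the plan says.** The plan defines an AE in three ways.

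- **Sections 8.2 and 8.3.1**, in the same words: "Adverse events are considered events that are not already described as routine research risks in the consent form". Both go on: "We will not report pain at time of the biopsy as an AE, nor will we report bruising from biopsy or line placement procedures". The reason given is that these events are almost certain to occur in every participant.
- **Section 8.1**: "An untoward or undesirable experience associated with the use of a medical product". There is no exclusion for expected events.
- **Section 10.1, IV.A**: "An adverse event (AE) is any untoward medical occurrence in a subject temporally associated with participation in the clinical study". Again there is no exclusion.

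The worksheet in 8.3.1 has the field "If the adverse event was expected".

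The Safety Review Plan that opens section 8, repeated in 8.6 and in 10.1 (V.F), requires the annual report to address "whether adverse event rates are consistent with pre-study assumptions". The data-review tables in 9.3 and 10.1 (V.A) add a quarterly look at AE rates, with the Endocrine Research Committee as independent monitor.

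Some expected harms are captured outside the AE log. Section 3.6 documents the duration and severity of symptoms during the niacin infusion. Section 3.7 lists flushing on the case report form and on a visual analogue scale in the medical record. Section 10.1 (IV.D) keeps a record of adverse reactions to biopsies and acts on it: "If an increase in the number of adverse reactions relative to historical controls is observed during the course of a particular study", technique is reassessed.

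**The concern.** Comparing an AE rate with what was assumed beforehand requires counting the events that were assumed. The 8.2 rule takes out of the count those that the consent form calls routine. Section 8.2 also promises to record all AEs, but that promise follows the narrowed definition and does not widen it.

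Two members of staff could therefore fill in the log differently, one following 8.2 and the other 10.1, and both would comply with the protocol. The annual and committee reviews would then rest on counts whose meaning depends on which section was followed. An excess of an expected but non-serious harm could go unseen in the AE rates.

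**Working it through.** The plan states no figure on this point, so there is nothing to reproduce. The check sets the definitions, the capture rules and the reviews side by side.

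**1. Definitions.** Sections 8.2 and 8.3.1 decide AE status by whether the consent form already describes the event as a routine risk. Sections 8.1 and 10.1 (IV.A) do not. They are not identical to each other either: 8.1 ties the event to use of a medical product, whereas 10.1 covers anything temporally associated with participation. Section 8.3.1 is also at odds with itself, because a field for expectedness presupposes that expected events can be AEs.

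**2. Which named risks have a record outside the AE log?**

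| Risk named in 1.5 or 10.1 (IV.D) | Separate event record | Stated to enter AE summaries? |
|---|---|---|
| Flushing, itching, nausea or vomiting during niacin | Yes (3.6; flushing also 3.7) | No |
| Muscle-biopsy haematoma, infection, numbness | Yes (10.1, IV.D) | No |
| Hypoglycaemia with insulin | None; 6.2 measures glucose every 10 minutes, but no text turns a low value into an event | No |
| Phlebitis | None | No |
| Hand burn from the heated box | None | No |

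Insulin and glucose are given at both inpatient visits (schedule in section 6), so the hypoglycaemia row applies to the saline visit as well.

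**3. Illustration of the mechanism.** The only numeric expected rate below 100% is in 10.1 (IV.D): numbness in fewer than 1% of muscle biopsies.

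- Muscle biopsies, from 3.1 and 6.3: 20 participants × 2 visits × 2 biopsies = 80. This assumes that all complete and that biopsies are independent.
- Expected events are 80p. At the stated ceiling p = 0.01 this is 0.8. At an assumed p = 0.05 it is 4.0.
- P(at least 1) at p = 0.01 is 1 − 0.99^80 = 0.55.
- P(at least 3) = 1 − Σ C(80,k) p^k (1−p)^(80−k), summed over k = 0, 1, 2.
  - p = 0.01: 1 − (0.448 + 0.362 + 0.144) = 0.047.
  - p = 0.05: 1 − (0.017 + 0.070 + 0.145) = 0.77 (from unrounded terms).

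Three or more cases would thus be a usable signal. If the consent form lists numbness as routine, the AE count under 8.2 is 0 at either rate. The separate biopsy record would show the cases, which is why it matters whether that record reaches the summaries. The 5% is an assumption for illustration, not a prediction.

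**4. Grading scales.**

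- Severity: 8.2 cites CTCAE 4.03. The 8.3.1 worksheet refers to a 1–5 scale, while the Severity Index in 8.3.1 has three levels. Section 10.1 (IV.B) has three levels defined differently.
- Attribution: the Relationship Index in 8.3.1 has five levels and concerns the drug. In 10.1 (IV.C), "they will be labeled either definitely, probably, possibly or unrelated to the study intervention", which makes four levels with no category for unlikely.

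**The case against.** The strongest defence is a narrow reading. The exclusion turns on the word routine, and the sentence that follows names only biopsy pain and bruising. Those are also the only risks that the documents expressly place in the consent form (10.1, IV.D). Section 10.1 reports no muscle-biopsy infection in 20 years and puts numbness below 1%, and neither is naturally called routine. On this reading the expectedness field makes sense and the rule excludes little beyond the existing carve-out.

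This stands in part. The consent form cannot be consulted here, so a broad exclusion is not established. But the rule is written as a general definition, routine is left undefined, and the reason given for pain and bruising does not extend to other risks. The conflict with 8.1 and 10.1 remains.

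The second defence also has force. A reader might infer that expected harms are not counted at all. Sections 3.6, 3.7 and 10.1 (IV.D) contradict that, and 10.1 (IV.E) makes anticipated serious AEs reportable. (Section 8.3.1 words reporting to the ethics board more narrowly; that is a separate matter to reconcile.) What these provisions leave open is the link from the separate records to the AE summaries, and the risks that have no separate event record.

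**Conclusion.** The concern holds as an internal contradiction with a limited consequence. If 8.2 and 8.3.1 are followed as written, consent-listed routine, non-serious events are missing from the AE rates that the annual and committee reviews use. The number of events lost cannot be estimated from the documents; it depends on the consent form and on how routine is read. The exposure is clearest for clamp hypoglycaemia, phlebitis and hand burns, provided that the consent form treats them as routine.

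Two further inferences are tempting but unsupported.

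- **That the other safety checks cannot work.** Under 8.1, an unanticipated problem involving risk to subjects or others (UPIRTSO) must be serious as well as unanticipated and related, so non-serious omissions largely do not affect it. The stopping rules in 8.5 and 10.1 (V.D) refer to adverse effects that alter risk-benefit, at the investigator's discretion under 8.5. They are not tied to the 8.2 definition or to a count. The rate-increase report in 8.3.2 concerns serious suspected reactions, and the historical-control check on biopsies has its own record.
- **That the AE table would read near zero.** This needs the broadest reading of routine and a consent form that lists every named risk as such. Neither can be shown.

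The differing severity and attribution scales are a secondary point. They make tabulations by grade or relatedness ambiguous, but no decision in the plan is shown to turn on them.

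**What to change.** 1. Delete the consent-form exclusion sentence from 8.2 and 8.3.1.
2. Use the 10.1 (IV.A) definition throughout, aligning 8.1 with it, and record expectedness as an attribute of each event in the existing worksheet field.
3. Keep only the carve-out already written for biopsy pain and for bruising from biopsy or line placement.
4. State that the niacin-symptom and biopsy-reaction records enter the 6-month and annual AE summaries.
5. As a tidy-up, name one severity scale and one attribution scale for all AE forms.

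The cost is revised wording and a few more lines on the AE log. The reported AE count will look less favourable. No dose, visit, procedure or sample size changes.
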